20.3 Adult Vaccine Reaction Diary

ACV01 Vaccine Reaction Diary Card

Participant ID: _____

Study Doctor: _____

Phone Number: _____

Call the Study Doctor listed above:

- If you have a temperature equal to or greater than 102.4 °F
- If you have any severe symptom that prevents daily activity or requires medical care
- If injection site symptoms are noted larger than ring B on the measuring tool
- If you have any concerns or questions about completing the Diary Card or about any symptoms you are experiencing

PLEASE HAVE THIS DIARY CARD WITH YOU DURING EACH SCHEDULED CALL WITH STUDY STAFF

YOUR CALL IS SCHEDULED

ON: _____

AT: _____

AM / PM

TEMPERATURE RECORDING: Take and record your oral temperature daily. Aim to take your temperature at the same time each day. Record all temperatures in degrees Fahrenheit (°F).

Directions:

1. Wipe the thermometer clean with rubbing alcohol and rinse with cold tap water before and after each use.
2. Do not eat, drink any liquids, exercise, bathe, or smoke for at least 15 minutes before taking your temperature.
3. Press the On/Off button. You will see the last recorded temperature briefly. The thermometer is ready to use when it reads "Lo" and a blinking "°F" is visible.
4. Place the thermometer under your tongue as far back as you can comfortably put it. Keep your mouth closed and hold the thermometer in the same spot until the thermometer beeps.
5. Record the date, time (using a 12-hour clock with AM or PM), and temperature reading in the table below.
6. If you take your temperature more than once in a day, record the highest temperature.

	Day 1 (Vaccination)	Day 2	Day 3	Day 4	Day 5	Day 6	Day 7
Date (DD/MMM/YYYY)	____ / ____ / 202____	____ / ____ / 202____	____ / ____ / 202____	____ / ____ / 202____	____ / ____ / 202____	____ / ____ / 202____	____ / ____ / 202____
Time (HH:MM)	____ : ____  AM  PM	____ : ____  AM  PM	____ : ____  AM  PM	____ : ____  AM  PM	____ : ____  AM  PM	____ : ____  AM  PM	____ : ____  AM  PM
Temperature (°F)	_____. ____ °F						

ACV01 Vaccine Reaction Diary Card

Participant ID: _____

INJECTION SITE SYMPTOM RECORD: Using the measuring tool provided at the time of your injection, rate the symptoms you experience in the table below. For each injection site symptom listed, mark either *Not Present* or circle the appropriate letter. Every day you must select either *Not Present* or record a rating for each symptom listed.

Directions:

1. Center the measuring tool over the injection site.
2. Note the letter (A, B, C or D) of the ring that holds the widest point of redness and/or swelling / hardness.
3. Circle the letter corresponding to each symptom in the table below. **Please select only one answer per box.**

Days After Vaccination	Day 1 (Vaccination)		Day 2		Day 3		Day 4		Day 5		Day 6		Day 7	
Date (DD/MMM/YYYY)	____/____/202____		____/____/202____		____/____/202____		____/____/202____		____/____/202____		____/____/202____		____/____/202____	
Injection Site Redness	 Not Present													
Injection Site Swelling / Hardness	 Not Present													

MEDICATION CHANGES: Have you changed or added any new medications this week (prescription and/or over-the-counter)?

Yes

No

If yes, record each new or updated medication below. If you need more space, record medications on a separate piece of paper and keep it with your diary.

Medication Name	Dose	Frequency	Start Date (DD/MMM/YYYY)	Stop Date (DD/MMM/YYYY)	Reason

ACV01 Vaccine Reaction Diary Card

Participant ID: _____

SYMPTOMS EXPERIENCED: Using the participant symptom rating scale provided, rate the symptoms you experience in the table below. If you have no symptoms, place an "X" in the *No Symptoms* box and leave all other boxes for that day blank. If you have one or more of the listed symptoms, use the rating scale to rate each symptom. Every day you must check either *No Symptoms* or record a rating (at minimum the applicable number: 0, 1, 2, 3; you may also write none, mild, moderate, or severe) for all of the symptoms listed. **CALL THE STUDY DOCTOR IF YOU EXPERIENCE ANY SEVERE (RATING #3) SYMPTOMS.**

SYMPTOM RATING SCALE:

- 0 No symptoms
- 1 Mild (present, but did not require over-the-counter or prescription medications; did not interfere with daily activities)
- 2 Moderate (required over-the-counter or prescription medications; caused some interference with daily activities)
- 3 Severe (required over-the-counter or prescription medications; significant, incapacitating discomfort preventing daily activities)

Days After Vaccination	Day 1 (Vaccination)	Day 2	Day 3	Day 4	Day 5	Day 6	Day 7
Date (DD/MMM/YYYY)	____/____/202____	____/____/202____	____/____/202____	____/____/202____	____/____/202____	____/____/202____	____/____/202____
No Symptoms							
Injection Site Reactions:							
Pain at Injection Site							
Redness at Injection Site							
Swelling / Hardness at Injection Site							
Papules							
Ulceration							

ACV01 Vaccine Reaction Diary Card

Participant ID: _____

Days After Vaccination	Day 1 (Vaccination)	Day 2	Day 3	Day 4	Day 5	Day 6	Day 7
Other:							
Lymph Node – Arm pit							
Chills							
Muscle Aches/Pain							
Joint Pain							
Tiredness / Fatigue							
Headache							
Nausea							
Vomiting							
Hives							
Diarrhea							
Shortness of Breath							
Chest Pain							
Pain (in arm)							
Pain (in leg)							
Swelling (in arm)							
Swelling (in leg)							

ACV01 Vaccine Reaction Diary Card

Participant ID: _____

ADDITIONAL SYMPTOMS:

Have you experienced any other symptoms (including an increase in symptoms in your underlying autoimmune disease) not listed above? Yes No

If Yes, record the symptoms you experienced. If you need more space, record symptoms on a separate piece of paper and keep it with your diary.

* Use the Symptom Rating Scale on page 3 and record only the highest rating experienced for that symptom between the start and stop dates (i.e., a headache rated 2 on Day 1 that increases to a 3 on Day 2 would be marked as a 3).

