Symptoms of myocarditis or pericarditis include chest pain, shortness of breath, or feelings of having a fast-beating, fluttering, or pounding heart, with onset of symptoms most commonly reported within a few days following vaccination. Symptoms may differ in younger pediatric populations, particularly in the 6 month to <5 year age group, and may include respiratory distress, fainting, irritability, lethargy, unusual and persistent cool, pale skin, or nonspecific gastrointestinal symptoms (poor feeding, abdominal pain, and vomiting). If any of these symptoms occur following vaccination, study participants should seek immediate medical attention and notify study site staff. Participants reporting acute chest pain, shortness of breath, palpitations, or other signs or symptoms of myocarditis or pericarditis within 6 weeks after vaccination must be referred to a cardiologist for evaluation and management.

Syncope may occur with the administration of vaccines, particularly in adolescents.

Two SAEs of facial swelling in individuals with a history of injection of dermatological fillers were reported following administration of the Moderna vaccine and were deemed as likely related to vaccine administration.

SPIKEVAX (COVID-19 Vaccine, mRNA) and Moderna COVID-19 Vaccine can be used interchangeably. Moderna COVID-19 Vaccine, Bivalent is made in the same way as SPIKEVAX and Moderna COVID-19 Vaccine, but it also contains an Omicron component to help prevent COVID-19 caused by the Omicron variant of SARS-CoV-2. Safety data with Moderna COVID-19 Vaccine are relevant to Moderna COVID-19 Vaccine, Bivalent because these vaccines are manufactured using the same process.

COMIRNATY (COVID-19 Vaccine, mRNA) and the Pfizer-BioNTech COVID-19 Vaccine, when prepared according to their respective instructions for use, can be used interchangeably. The Pfizer-BioNTech COVID-19 Vaccine, Bivalent is made in the same way as COMIRNATY and Pfizer-BioNTech COVID-19 Vaccine but it also contains an Omicron component to help prevent COVID-19 caused by the Omicron variant of SARS-CoV-2. Safety data with Pfizer-BioNTech COVID-19 Vaccine are relevant to Pfizer-BioNTech COVID-19 Vaccine, Bivalent because these vaccines are manufactured using the same process.

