ACV01 Pediatric Diary Card (2 year old)

Participant ID: _____

INJECTION SITE SYMPTOM RECORD: The site coordinator will provide you with the appropriate measuring tool based upon participant age (2-4 year old measuring tool). Using the measuring tool provided at the time of your child's injection, rate the symptoms you experience in the table below. For each injection site symptom listed, mark either *Not Present* or circle the appropriate letter. Every day you must select either *Not Present* or record a rating for each symptom listed.

Directions:

1. Center the measuring tool over the injection site.
2. Note the letter (A, B, C or D) of the ring that holds the widest point of redness and/or swelling / hardness.
3. Circle the letter corresponding to each symptom in the table below. **Please select only one answer per box.**

Days After Vaccination	Day 1 (Vaccination)				Day 2				Day 3				Day 4				Day 5				Day 6			
Date (DD/MMM/YYYY)	____/____/202____				____/____/202____				____/____/202____				____/____/202____				____/____/202____				____/____/202____			
Injection Site Redness	 Not Present																							
Injection Site Swelling / Hardness	 Not Present																							
	A	B	C	D	A	B	C	D	A	B	C	D	A	B	C	D	A	B	C	D	A	B	C	D

MEDICATION CHANGES: Has your child changed or added any new medications this week (prescription and/or over-the-counter)?
If yes, record each new or updated medication below. If you need more space, record medications on a separate piece of paper and keep it with your diary.

Medication Name	Dose	Frequency	Start Date (DD/MMM/YYYY)	Stop Date (DD/MMM/YYYY)	Reason

ACV01 Pediatric Diary Card (2 year old)

Participant ID: _____

SYMPTOMS EXPERIENCED: Using the symptom rating scale provided, rate the symptoms your child experiences in the table below. If your child has no symptoms, place an "X" in the *No Symptoms* box and leave all other boxes for that day blank. If your child has one or more of the listed symptoms, use the rating scale to rate each symptom. Every day you must check either *No Symptoms* or record a rating (at minimum the applicable number: 0, 1, 2, 3; you may also write none, mild, moderate, or severe) for all of the symptoms listed. **CALL THE STUDY DOCTOR IF YOUR CHILD EXPERIENCES ANY SEVERE (RATING #3) SYMPTOMS.**

GENERAL SYMPTOM RATING SCALE:

- 0 No symptoms

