20.5 Pediatric Vaccine Reaction Diary (3 – 4 year old)

ACV01 Pediatric Diary Card (3 - 4 year old)

Participant ID: _____

Study Doctor: _____

Phone Number: _____

Call the Study Doctor listed above:

- If your child has a temperature equal to or greater than 102.4 °F
- If your child has any severe symptom that prevents daily activity or requires medical care
- If injection site symptoms are noted larger than ring B on the measuring tool
- If you have any concerns or questions about completing the Pediatric Diary Card or about any symptoms your child is experiencing

PLEASE HAVE THIS DIARY CARD WITH YOU DURING EACH SCHEDULED CALL WITH STUDY STAFF

YOUR CALL IS SCHEDULED

ON: _____

AT: _____

AM / PM

TEMPERATURE RECORDING: Take and record your child's oral temperature daily. Aim to take your child's temperature at the same time each day. Record all temperatures in degrees Fahrenheit (°F).

Directions:

1. Wipe the thermometer clean with rubbing alcohol and rinse with cold tap water before and after each use.
2. Do not have them eat, drink any liquids, exercise, or bathe for at least 15 minutes before taking their temperature.
3. Press the On/Off button. You will see the last recorded temperature briefly. The thermometer is ready to use when it reads "Lo" and a blinking "°F" is visible.
4. Place the thermometer under your child's tongue as far back as you can comfortably put it. Keep your child's mouth closed and hold the thermometer in the same spot until the thermometer beeps.
5. Record the date, time (using a 12-hour clock with AM or PM), and temperature reading in the table below.
6. If you take your child's temperature more than once in a day, record the highest temperature.

	Day 1 (Vaccination)	Day 2	Day 3	Day 4	Day 5	Day 6	Day 7
Date (DD/MMM/YYYY)	____ / ____ / 202____	____ / ____ / 202____	____ / ____ / 202____	____ / ____ / 202____	____ / ____ / 202____	____ / ____ / 202____	____ / ____ / 202____
Time (HH:MM)	____ : ____  AM  PM	____ : ____  AM  PM	____ : ____  AM  PM	____ : ____  AM  PM	____ : ____  AM  PM	____ : ____  AM  PM	____ : ____  AM  PM
Temperature (°F)	____ · ____ °F						

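### The printed diary cards tell participants to call for severe symptoms, while Section 5.1.1 asks for immediate care and site notification for any possible myocarditis or pericarditis symptom

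*Protocol*

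**What the plan says.** Protocol Section 5.1.1, on the mRNA vaccines, names chest pain, shortness of breath and a racing, fluttering or pounding heart. For young children it adds respiratory distress, fainting, irritability, lethargy, skin that stays unusually cool and pale, and nonspecific gastrointestinal symptoms. It then states: "If any of these symptoms occur following vaccination, study participants should seek immediate medical attention and notify study site staff". Participants who report such symptoms "within 6 weeks after vaccination must be referred to a cardiologist for evaluation and management". The same section says that onset is usually within a few days of vaccination.

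The diary cards cover the first seven days. Under a heading that tells the reader to call the study doctor, the adult card (Appendix 20.3) lists four triggers:

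- a temperature of 102.4 °F or more;
- "If you have any severe symptom that prevents daily activity or requires medical care";
- an injection-site reaction larger than ring B;
- "If you have any concerns or questions about completing the Diary Card or about any symptoms you are experiencing".

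Above the symptom grid it adds, in capitals, "CALL THE STUDY DOCTOR IF YOU EXPERIENCE ANY SEVERE (RATING #3) SYMPTOMS". The three pediatric cards follow the same pattern. Appendix 20.4 has "CALL THE STUDY DOCTOR IF YOUR CHILD EXPERIENCES ANY SEVERE (RATING #3) SYMPTOMS" and Appendix 20.5 has "If your child has any severe symptom that prevents daily activity or requires medical care".

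Shortness of breath is a daily row on all four cards. Chest pain is a row on the adult and 5 to 17 year cards only. Palpitations and fainting are rows on none.

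**The concern.** Section 5.1.1 directs its instruction at participants, but the printed form they use during the week of likeliest onset sets a higher bar. The adult and 5 to 17 year cards ask people to rate chest pain and shortness of breath each day, then single out rating 3 as the reason to telephone. A literal reader could conclude that a lower rating can wait.

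What is at stake is prompt evaluation. Several duties start only when the site learns of the event: cardiology referral (Section 5.1.1), reporting of adverse events of special interest within 24 hours of discovery (Section 12.5.2), and notice to the DSMB chair within 3 business days of that report (Section 11.5).

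**Working it through.** The plan states no figure on this point, so the check sets the texts side by side. The only arithmetic is the time to the scheduled review.

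**Step 1: the rule.** Section 5.1.1 is triggered by any listed symptom, at any severity. The action is immediate care plus notice to the site. The myocarditis case definition in Appendix 20.8 likewise puts no severity floor on chest pain.

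**Step 2: a test case on the adult card.** Take an adult with chest pain on Day 3 who uses an over-the-counter painkiller and is somewhat limited. The card's scale makes this rating 2: "Moderate (required over-the-counter or prescription medications; caused some interference with daily activities". Going through the call instructions:

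- Temperature: not met.
- Ring B: not met.
- Rating 3: not met, because that rating requires discomfort that prevents daily activities.
- Severe symptom that prevents activity or requires medical care: not clearly met. The reference to medical care qualifies a severe symptom, and the reader must already know that chest pain needs care. The card does not say so.
- Concerns or questions: met only if the participant is worried enough to call.

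No line tells this person to seek care. The Section 5.1.1 rule is met in full.

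**Step 3: a test case on the under-5 cards.** Vomiting more than twice in 24 hours that does not prevent daily activity is rated moderate on Appendices 20.4 and 20.5. Vomiting is among the young-child signs in Section 5.1.1, so the same gap appears. This sign is far less specific, which matters for the fix.

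**Step 4: time to the first scheduled diary review.** Delay = review day − onset day. The review is on Day 8 to 12 in Sections 8.1.1, 8.2.1, 8.3.1 and 8.4.1, and on Day 7 to 15 in the pediatric schedules (Tables 20 to 22). Onset on Day 2 to 4 is an assumed reading of a few days.

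| Onset | Review Day 8–12 | Review Day 7–15 |
|---|---|---|
| Day 2 | 6–10 days | 5–13 days |
| Day 3 | 5–9 days | 4–12 days |
| Day 4 | 4–8 days | 3–11 days |
| Overall | 4–10 days | 3–13 days |

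These are gaps for someone who neither calls nor seeks care before the review. They are not predicted delays.

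**The case against.** The strongest reply is that nothing obliges the card to carry the warning. Section 5.1.1 names no vehicle for it, and Section 8.1.4.1 describes the diary as a recording aid. Risk warnings normally reach participants through consent, which Section 17.2 says is revised when important safety information emerges. The consent pages, e-diary screens and Manual of Procedures are not in the reviewed text. Section 8.1.4.1 also makes the electronic diary the main tool: paper may be given to people without a device or as a backup. The 2 year old card is footed as a working version.

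That limits the point to the printed cards. A reader might infer that participants are never warned about cardiac symptoms, or that the plan breaks a stated requirement; the documents support neither. What remains is that the printed threshold disagrees with the protocol's own rule, and would still disagree if the warning appears elsewhere.

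The concerns-or-questions line sits under the same call heading as the fever trigger, so a worried participant may well telephone early. Section 8.1.5 adds that participants should be told to contact staff when concerns arise, and staff go through the diary with each participant. These safeguards soften the consequence. None names the symptoms, and each relies on the participant seeing their importance.

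Section 5.1.1 concerns mRNA vaccines, while the adult card also serves Sanofi-GSK recipients. But Section 12.4.1 collects myocarditis and pericarditis in every arm, so a common line does no harm.

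**Conclusion.** The point holds for the cards as printed in Appendices 20.3 to 20.6. A participant with mild or moderate chest pain or shortness of breath who follows the card is not told to act before the Week 1 review, whereas Section 5.1.1 asks for action at once. The illustrative gap of 4 to 10 days, or 3 to 13 days under the pediatric tables, rests on the assumed onset days and on no earlier contact.

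A reader might go further and infer that cases will be missed or the event count biased. The documents do not support that: the Week 1 review would bring the diary entry to light, and Grade 2 or higher myocarditis and pericarditis are collected to the end of participation. The risk is late evaluation. The Week 4 antibody endpoint and the sample size are unaffected. This is a cheap safety improvement, worth making at the next revision of the cards.

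**What to change.** Add one line to the call list on all four cards, and to the e-diary if it is not already there: *Seek medical care right away and call the Study Doctor, whatever the rating, for chest pain, shortness of breath, a fast, fluttering or pounding heart, or fainting.*

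On the two under-5 cards, extend the seek-care line only to the more specific signs in Section 5.1.1: respiratory distress, fainting, lethargy, and skin that stays unusually cool and pale. For irritability, poor feeding, abdominal pain or vomiting, ask families to call the study doctor promptly. Several of these are also ordinary vaccine reactions at that age (Section 1.4), and sending every such child for care would be disproportionate.

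Do not add palpitations or fainting as solicited rows. Section 12.3.2 attributes every solicited event to the vaccine; left unsolicited, these stay subject to investigator attribution.

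The cost is some extra calls and unscheduled visits. A visit judged possibly related to vaccine is an MAAE under Section 12.2.4, and a solicited event that becomes one must be entered in the data capture system (Section 12.5.1). MAAE counts, part of a secondary safety endpoint, may therefore rise after the change, so its date should be recorded and noted when those counts are reported. No new scheduled visit or procedure is needed.

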12.2.1.3 Solicited Adverse Events (Reactogenicity)

Solicited AEs are predefined local and systemic events for which the participants will be specifically questioned, and which will be noted by these participants. In this study, queried symptoms will include:

- Injection site reaction such as pain, erythema, induration/edema as well as development of papules, and ulceration.
- Axillary lymphadenopathy.
- Solicited systemic reactions including fever (assessed as daily oral temperature), chills, myalgia, arthralgia, fatigue*, headache*, nausea*, vomiting, hives, and diarrhea.

*Participants that are 2-3 years old will have sleepiness, irritability/crying, and loss of appetite assessed rather than fatigue, headache, and nausea.

- Increased shortness of breath, chest pain**, swelling/pain in arm or leg**.

**These symptoms will be assessed in participants age 5 years and above.

- Increase in symptoms of the participant's underlying autoimmune disease.

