12.4.2 Increase in Autoimmune Disease Activity

Any increase in autoimmune disease activity (flare/relapse) for the participant's qualifying autoimmune disease will not be reported as an AE. These events will be collected and reported on the disease-specific assessment eCRFs. (Section 8.1.4.2 Disease-Specific Assessments).

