- 1 Mild (present, but did not require over-the-counter or prescription medications; did not interfere with daily activities)
- 2 Moderate (required over-the-counter or prescription medications; caused some interference with daily activities)
- 3 Severe (required over-the-counter or prescription medications; significant, incapacitating discomfort preventing daily activities)

Days After Vaccination	Day 1 (Vaccination)	Day 2	Day 3	Day 4	Day 5	Day 6	Day 7
Date (DD/MMM/YYYY)	__ / __ / 202__	__ / __ / 202__	__ / __ / 202__	__ / __ / 202__	__ / __ / 202__	__ / __ / 202__	__ / __ / 202__
No Symptoms							
Injection Site Reactions:							
Pain at Injection Site							
Redness at Injection Site							
Swelling / Hardness at Injection Site							
Papules							
Ulceration							

Instructions for Other Symptoms: Grade using the General Symptom Rating Scale above, with the following exceptions:	SYMPTOM-SPECIFIC RATING SCALE: VOMITING	SYMPTOM-SPECIFIC RATING SCALE: DIARRHEA
	0 No symptoms 1 Mild: 1 to 2 times in 24 hours 2 Moderate: >2 times in 24 hours 3 Severe: Prevents daily activity	0 No symptoms 1 Mild: 2 to 3 loose stools in 24 hours 2 Moderate: 4 to 5 loose stools in 24 hours 3 Severe: 6 or more loose stools in 24 hours

ACV01 Pediatric Diary Card (2 year old)

Participant ID: _____

Days After Vaccination	Day 1 (Vaccination)	Day 2	Day 3	Day 4	Day 5	Day 6	Day 7
Other:							
Lymph Node – Arm pit							
Chills							
Muscle Aches/Pain							
Joint Pain							
Sleepiness (Tiredness / Fatigue)							
Irritability/Crying (Headache)							
Loss of Appetite (Nausea)							
Vomiting							
Hives							
Diarrhea							
Shortness of Breath							
Swelling in arm							
Swelling in leg							

ADDITIONAL SYMPTOMS: Has your child experienced any other symptoms (including an increase in symptoms in their underlying autoimmune disease) not listed above? Yes No

National Institute of Allergy and Infectious Diseases | Protocol ACV01
 © 2014 Rho, Inc., [name]. All rights reserved. No part of this document may be copied without expressed written permission

Pediatric Participant Diary Card | Version 1.0 | WORKING
 Page 4 of 5

ACV01 Pediatric Diary Card (2 year old)

Participant ID: _____

If Yes, record the symptoms they experienced. If you need more space, record symptoms on a separate piece of paper and keep it with your diary.

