Instructions for Other Symptoms: Grade the other symptoms noted below using the General Symptom Rating Scale above, with the following exceptions:

SYMPTOM-SPECIFIC RATING SCALE: b NAUSEA / VOMITING	SYMPTOM-SPECIFIC RATING SCALE: c DIARRHEA
0 No symptoms	0 No symptoms
1 Mild: 1 to 2 times in 24 hours	1 Mild: 2 to 3 loose stools in 24 hours
2 Moderate: >2 times in 24 hours	2 Moderate: 4 to 5 loose stools in 24 hours
3 Severe: Prevents daily activity	3 Severe: 6 or more loose stools in 24 hours

ACV01 Pediatric Diary Card (5-17 year old)

Participant ID: _____

Days After Vaccination	Day 1 (Vaccination)	Day 2	Day 3	Day 4	Day 5	Day 6	Day 7
Other:							
Lymph Node – Arm pit							
Chills							
Muscle Aches/Pain							
Joint Pain							
Tiredness / Fatigue							
Headache							
Nausea ^b							
Vomiting ^b							
Hives							
Diarrhea ^c							
Shortness of Breath							
Chest Pain							
Pain in arm							
Pain in leg							
Swelling in arm							
Swelling in leg							

ACV01 Pediatric Diary Card (5-17 year old)

Participant ID: _____

ADDITIONAL SYMPTOMS: Have you or your child experienced any other symptoms (including an increase in symptoms in your underlying autoimmune disease) not listed above?

Yes

No

If Yes, record the symptoms experienced. If you need more space, record symptoms on a separate piece of paper and keep it with your diary.

Symptom Experienced	Highest Rating Experienced*	Start Date (DD/MMM/YYYY)	Stop Date (DD/MMM/YYYY)

* Use the Symptom Rating Scale on page 3 and record only the highest rating experienced for that symptom between the start and stop dates (i.e., a headache rated 2 on Day 1 that increases to a 3 on Day 2 would be marked as a 3).

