9.2.1. Solicited Adverse Events

Participants are provided access to an electronic 7-day diary to aid in recording solicited local and systemic reactions to the vaccine, as well as symptoms of a potential allergic reaction, unsolicited AEs, and concomitant medications, including start and stop dates. The diary includes instructions for participants on how to take an oral temperature and how to measure injection site reactions. A paper copy of the diary may be provided for participants who do not have a device to access the electronic diary or as a backup collection tool. A member of the study team will review the information in the diary with the participant, including how to use and access the electronic diary, and will record adverse events on the CRF page as appropriate based on review of the diary.

Summary displays based on the maximum severity of solicited symptoms reported over the 7-day period will be presented in tables and graphically by study arm. Summaries of the diary entries over the 7-day period will also be presented by study arm.

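### Worsening autoimmune disease is a solicited event with no diary item of its own, so early worsening that shows as joint pain, muscle pain or tiredness is not reliably recorded as disease worsening

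*Protocol*

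**What the plan says.** Protocol Section 12.2.1.3 defines solicited events as "predefined local and systemic events for which the participants will be specifically questioned". Its list ends with "Increase in symptoms of the participant's underlying autoimmune disease". Separately, it names systemic reactions that include "chills, myalgia, arthralgia, fatigue*, headache*, nausea*, vomiting, hives, and diarrhea".

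The adult card (Section 20.3) has a daily 0–3 grid, followed by one Yes/No item: "Have you experienced any other symptoms (including an increase in symptoms in your underlying autoimmune disease) not listed above". The cards for age 2 (Section 20.4) and ages 3–4 (Section 20.5) ask "Has your child experienced any other symptoms (including an increase in symptoms in their underlying autoimmune disease) not listed above". The card for ages 5–17 (Section 20.6) asks "Have you or your child experienced any other symptoms (including an increase in symptoms in your underlying autoimmune disease) not listed above". Only the pronouns differ.

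Four other rules decide what happens to an answer:

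- Section 12.2.2 calls an event unsolicited only if it comes from an open-ended question and is not specified as solicited.
- Section 12.3.2 attributes every solicited event to the study vaccine.
- Section 12.4.2 says that a flare or relapse of the participant's "qualifying autoimmune disease will not be reported as an AE" and sends it to the disease-specific assessment eCRFs.
- SAP Section 9.2.1 plans "Summary displays based on the maximum severity of solicited symptoms reported over the 7-day period", by study arm.

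**The concern.** The protocol promises a specific question about disease worsening, and the cards ask it inside a catch-all restricted to symptoms not already on the page. For a participant whose disease shows as joint pain, muscle pain or fatigue, the symptom is on the page. Having rated it there, the participant can reasonably answer No to the catch-all.

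This matters because of the medication hold. Section 5.3.1 says that withdrawing the immunosuppressant could lead to exacerbation and flare. Whether disease activity rises after the dose is a secondary objective in both stages (Sections 2.2.1 and 2.2.2). If early worsening is logged as ordinary joint pain, an effect of the hold or of the disease is counted as vaccine reactogenicity, and the two cannot be separated afterwards.

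**Working it through.** There is no plan figure to reproduce. The check sets the passages side by side.

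**1. Does each card carry the item?**

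| Check | Cards |
|---|---|
| Disease worsening has its own daily row | 0 of 4 |
| Disease worsening appears only in the catch-all | 4 of 4 |
| Grid above already lists joint pain, muscle pain and tiredness | 4 of 4 |

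On the age-2 card, tiredness appears as sleepiness, with tiredness/fatigue in brackets.

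**2. Where does an answer go?** Take a participant with RA whose joints worsen on Day 3.

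- *Rates joint pain and answers No.* The event is solicited arthralgia, vaccine-related under Section 12.3.2, and enters the SAP 9.2.1 display as joint pain. Nothing marks it as disease.
- *Answers Yes and writes it in.* The entry has a highest rating with start and stop dates (table shown on the Section 20.5 and 20.6 cards), not a daily rating. Its class is unclear. Section 12.2.1.3 makes it solicited, so it fails the unsolicited definition in Section 12.2.2. Section 12.3.2 then makes it vaccine-related. Section 12.4.2 says that increased activity of the qualifying disease is not reported as an AE at all.

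On either path, the SAP 9.2.1 seven-day display has no clean variable for this event.

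**3. Which diseases overlap with the grid?** Section 13.1 lists 5 adult and 4 pediatric diseases, so 5 + 4 = 9 labels. The overlap is RA (joint pain), JIA (joint pain), JDM (muscle pain), and adult and pediatric SLE (joint pain, fatigue): 1 + 1 + 1 + 2 = 5 of 9. This mapping is a judgement; the documents give none. MS and POMS are left out because Sections 12.8.2.2.1 and 12.8.2.2.2 do not accept fatigue as enough to establish a relapse.

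**4. Timing.** The diary covers Days 1–7. Section 7.1.1 sets the post-dose hold at 10 days for MMF/MPA and at least 7 days for MTX, so for participants who withhold, the whole diary falls inside it. With vaccination on Day 1, Week 4 is Day 1 + 28 = Day 29, and the window opens at 29 − 7 = Day 22. The schedules in Section 20.1 show no disease-specific or global assessment between Baseline and that visit.

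**The case against.** The strongest reply is that worsening has several other routes. Every card names it and allows a Yes; since no row is called disease worsening, a participant may well regard it as not yet listed. Staff review the diary at Week 1. Solicited events still ongoing at Day 7 go into EDC and are followed (Section 12.5.1). Participants are to be told to contact the site if disease activity rises (Section 8.1.5), and such a visit requires all disease-specific assessments (Section 20.1). Section 12.4.2 routes flares to their own forms, SAP 8.3.7 summarises flares by Week 4, and severe flare triggers DSMB review. Nothing requires a 0–3 row for each solicited event: fever has only a temperature log.

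Most of this stands, and it defeats three readings that a reader might infer:

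- *That worsening is never recorded.* The write-in and the other routes contradict this.
- *That the diary is the only scheduled look before Week 4.* The Week 1 review is also scheduled, although it starts from the same card.
- *That the item would yield almost no events.* The documents hold no data on how participants answer.

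It does not remove the narrower point. Fever at least has its own field. The backstops depend on the participant's initiative, on the symptom lasting, or on later visits, and none supplies the seven-day solicited variable. Section 12.4.2 could be read as covering flare rather than symptoms, but the documents draw no such line.

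**Conclusion.** The point holds as a gap in data collection. A named solicited event lacks its own item on all four cards, and Day 1–7 worsening that shows as a listed symptom is not reliably recorded as disease worsening. It bears most on 5 of 9 disease labels. The size of any undercount cannot be estimated from the documents.

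The concern about the hold applies only to participants who withhold; continue arms, and participants on B cell depletion without MMF/MPA or MTX, have no hold. The conclusion also assumes that the e-diary, which is the primary tool under Section 8.1.4.1 and whose screens are not in the documents, follows the printed cards. The change is a cheap improvement worth making; disease activity is not left unmonitored without it.

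**What to change.** 1. **Cards and e-diary.** Add one daily 0–3 row to all four versions: *Increase in symptoms of your (child's) autoimmune disease – rate this even if you also recorded the symptom above.* Remove the bracketed phrase from the catch-all.
2. **Protocol.** Reconcile Sections 12.2.1.3 and 12.3.2 (solicited, automatically vaccine-related) with Section 12.4.2 (worsening of the qualifying disease not reported as an AE). State that this row is tabulated on its own as disease worsening, without automatic vaccine attribution, and is not counted again as joint pain or fatigue. Without this step the new row would inherit the present conflict.
3. **SAP Section 9.2.1.** Display the row by disease. Split it by withhold/continue plan only in the randomised Stage 1 Cohorts A and B. Adult Stage 1 is closed and Stage 2 withholds MMF/MPA or MTX in everyone taking it, so prospectively this means Pediatric Stage 1.

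The cost is one more daily question and one display. It changes no dose, hold or clinical rule, and it cannot recover the item from diaries already completed.
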